7.2.15 Sponsor Responsibility for Reporting Adverse Events

All Adverse Events will be reported to regulatory authorities, IRB/IECs and investigators in accordance with all applicable global laws and regulations.

8.0 STATISTICAL ANALYSIS PLAN

8.1 Statistical Analytical Plan Summary

8.1.1 Statistical Analysis Plan Phase I

Phase I lead-in considerations:

Cohort 1: doxorubicin + pembrolizumab

Drug	Doxorubicin	Pembrolizumab
Level 1	50 mg/m ²	200 mg
Level 2	60 mg/m ²	200 mg

Cohort 2: AI + pembrolizumab (AIs are combined for the safety/activity primary endpoints)

Drug	Anti-estrogen	Pembrolizumab
Level 1	Standard*	200 mg

* Exemestane 25 mg daily po preferred, Anastrozole 1 mg daily po, or letrozole 2.5 mg daily po are options.

8.1.1.1 Safety Lead-in and Dose Escalation and De-escalation

For both cohorts we will have a safety lead-in employing a 3-at-risk rolling design. For each treatment, we will permit only 3 patients to be at risk for first cycle toxicities at any one time during the safety-lead in.

8.1.1.1.1 Cohort 1 (Pembrolizumab and Doxorubicin)

For cohort 1, a dose escalation from 50mg/m² to 60mg/m² will be permitted according the 3-at-risk dose escalation rules (below). There will not be intra-patient dose-escalation. Once the safety lead-in is complete, accrual will proceed based on the phase II considerations for cohort 1 below. Any dose de-escalation from 50mg/m² will require discussion with the sponsor and an amendment.

8.1.1.1.2. Cohort 2 (pembrolizumab and Aromatase Inhibitor)

For cohort 2, when the first 6 patients have been completed cycle 1 with at most 1 dose limiting toxicities (DLT), the safety-lead in for that doublet will be considered successful, and accrual will proceed based on the Phase II considerations below. For cohort 2, if 2 DLTs are observed on dose level 1 in the first 6 patients the study will hold accrual pending discussion with sponsor, PI, and COH DSMB for the selection of a dose level -1 or terminate consideration of that treatment doublet.

8.1.2 Definitions of DLTs

DLTs for both cohorts are defined as:

Hematologic Toxicities:

- Any Grade 4 thrombocytopenia or neutropenia lasting >7 days

Nonhematologic Toxicities:

- Episcleritis, uveitis, or iritis of Grade 2 or higher

- Any Grade 4 toxicity

- Any Grade 3 toxicity EXCLUDING:

- Nausea, vomiting, or diarrhea controlled by medical intervention within 72 hours
 - Grade 3 rash in the absence of desquamation, no mucosal involvement, does not require steroids, and resolves to Grade 1 by the next scheduled dose of pembrolizumab.
 - Rapidly reversible electrolyte abnormalities (within 72 hrs.).
 - Transient Grade 3 AST or ALT elevation, defined as no more than 3 days with or without steroid use

- Discontinuation or delay of more than 2 weeks of any study drug due to treatment-related AE will be considered as a DLT

Toxicity will be graded according to the NCI CTCAE version 4.0. To be evaluable for toxicity, a patient must receive at least one complete course of treatment and be observed for at least 21 days after the start of the first course or have experienced a DLT. All patients who receive any amount of drug will be considered evaluable for toxicity.

8.1.3 3-at-risk—Rules of Level Assignment

3-at-risk -- Rules for Dose Level Assignment

# Patients on Current Level			Action
DLT	EVAL	EVAL+At Risk	
0	0	1-2	Accrue next patient at this level*
0	0	3	Hold accrual
0	1	1-3	Accrue next patient at this level
0	1	4	Hold accrual
0	2	2-4	Accrue next patient at this level
0	2	5	Hold accrual
0	3	3-5	Accrue next patient at the next higher level*
1	1	1-2	Accrue next patient at this level
1	1	3	Hold Accrual
1	2	2	Accrue next patient at this level
1	2	3-4	Hold accrual
1	3-5	3-5	Accrue next patient at this level
1	3-5	6	Hold accrual
1	6	6	Accrue next patient at the next higher level*
2**	any	Any	Accrue next patient at the next lower level to a maximum of 6

*If in dose-escalation portion. If higher dose level already closed, the next lower dose will accrue to a total of 6 patients, with 2 or higher DLTs requiring further dose de-escalation. If there is no next higher dose, the next patient will be accrued to the current level.
 
**Patients treated on a higher dose during cycle 1 will have their treatment modified to the dose below the dose level with 2 DLTs.
			

Note: “DLT” – a patient with a documented first-cycle DLT; “PASS” – a patient without a first-cycle DLT fully evaluable for toxicity for the purpose of dose escalations; “EVAL” – a patient who is either DLT or PASS; “Inevaluable” – a patient who is off treatment without being DLT or PASS; “At Risk” – a patient who is on study in the first cycle and not yet DLT, PASS, or Inevaluable

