4.1.5.2 Biomarker Research

Preliminary studies suggest that CD8 T cell infiltration and PD-L1 expression within tumors may predict efficacy for pembrolizumab, but definitive biomarkers are not yet available. To identify biomarkers to predict and/or follow efficacy for pembrolizumab in combination with other agents in metastatic breast cancer, we propose the following correlative studies to analyze the immune and stromal cells within metastatic tumors, as well as immune cells in peripheral blood, before and after therapy:

We will obtain archived biopsies or fresh biopsies as feasible of one or more metastatic lesion(s) before and one month post treatment. In addition, blood samples will be obtained at weeks 0, 2, 4, 6, 8, 10, 20, and 30 to track the temporal dynamics of the host immune response. Key questions we will address include:

1. Immune and stromal cells characteristics before treatment that correlate with clinical response.
2. Changes in immune and stromal cells after therapy that correlate with clinical response.

Approaches:

1. 12-color FACS analysis to enumerate/phenotype immune cell subsets and functional readouts, including cytokine production and signaling (phosflow)
2. TCR repertoire analysis via deep sequencing. Expansion of the T cell repertoire after therapy will be evidence for an immunological response and may indicate epitope spread.
3. Immunohistology using a novel quantitative, spatial image analysis system (Vectra, Perkin Elmer) that will enable us to analyze immune, stromal, and cancer cells in metastatic tumors via 8-color histology.
4. Gene expression analysis of stromal cells via RNA-Seq or microarrays.
5. Morphological / IHC TIL analysis of tumor biopsies.

Serial Cytokine Measurements

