5.3.2 Timing of Dose Administration

Trial treatment should be administered on Day 1 of each cycle after all procedures/assessments have been completed as detailed on the Trial Flow Chart (Section 6.0). Trial treatment may be administered up to 3 days before or after the scheduled Day 1 of each cycle due to administrative reasons.

All trial treatments will be administered on an outpatient basis.

Pembrolizumab 200 mg will be administered as a 30 minute IV infusion every 3 weeks. Sites should make every effort to target infusion timing to be as close to 30 minutes as possible. However, given the variability of infusion pumps from site to site, a window of -5 minutes and +10 minutes is permitted (i.e., infusion time is 30 minutes: -5 min/+10 min).

Follow the package insert for the preparation of the pembrolizumab infusion fluid and administration of infusion solution.

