6.0 TRIAL FLOW CHART

6.1 Study Flow Chart

Trial Period:	Screening Phase		Treatment Cycles								End of Treatment	Post-Treatment		
	Pre-screening (Visit 1)	Main Study Screening (Visit 2)	1	2	3	4	To be repeated beyond 8 cycles					Safety Follow-up	Follow Up Visits	Survival Follow-Up
Treatment Cycle/Title:							5	6	7	8				
Scheduling Window (Days):		-28 to -1		± 3	± 3	± 3	± 3	± 3	± 3	± 3	At time of Discont.	30 days post Discont.	Every 8 weeks post Discont.	Every 12 weeks
Administrative Procedures														
Pre-screening Consent	X													
Informed Consent		X												
Inclusion/Exclusion Criteria		X												
Demographics and Medical History		X												
Prior and Concomitant Medication Review		X	X	X	X	X	X	X	X	X		X		
Trial Treatment Administration			X	X	X	X	X	X	X	X				
Post-study anticancer therapy status													X	X
Survival Status														X
Clinical Procedures/Assessments														
Review Adverse Events		X	X	X	X	X	X	X	X	X		X		
Full Physical Examination		X												
Directed Physical Examination			X	X	X	X	X	X	X	X				
Vital Signs and Weight		X	X	X	X	X	X	X	X	X				
ECOG Performance Status		X	X	X	X	X	X	X	X	X				
Laboratory Procedures/Assessments: analysis performed by LOCAL laboratory														
Pregnancy Test – Urine or Serum β-HCG		X												
PT/INR and aPTT		X												
CBC with Differential		X	X	X	X	X	X	X	X	X		X		

Trial Period:	Screening Phase		Treatment Cycles								End of Treatment	Post-Treatment			
	Treatment Cycle/Title:	Pre-screening (Visit 1)	Main Study Screening (Visit 2)	1	2	3	4	To be repeated beyond 8 cycles				Discont.	Safety Follow-up	Follow Up Visits	Survival Follow-Up
Scheduling Window (Days):				-28 to -1	± 3	± 3	± 3	± 3	± 3	± 3	± 3				
Comprehensive Serum Chemistry Panel		X	X	X	X	X	X	X	X	X	X	X	X		
Urinalysis		X		X		X		X		X			X		
T3, FT4 and TSH		X		X		X		X		X			X		
Efficacy Measurements															
Tumor Imaging with CT (chest, abdomen, pelvis, bone scan, other modalities as deemed appropriate clinically)		X			X			X			X				
Cardiac evaluation: Echo, or MUGA and ECG for triple negative and MUGA or ECHO for the HR+ cohort		X								X@					
Tumor Biopsies/Archival Tissue Collection/Correlative Studies Blood															
Archival or Newly Obtained Tissue Collection		X		X#							X				
Correlative Studies Blood Collection##		X		X							X				
#optional ## if pts agree ask for weeks 4,6,8,10, 20,30															

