7.1.2.7 Tumor Tissue Collection and Correlative Studies Blood Sampling

Laboratory Procedures/Assessments

Details regarding specific laboratory procedures/assessments to be performed in this trial are provided below Laboratory Safety Evaluations (Hematology, Chemistry and Urinalysis)

Laboratory tests for hematology, chemistry, urinalysis, and others are specified in Table 5.

Table 5 Laboratory Tests

Hematology	Chemistry	Urinalysis	Other
Hematocrit	Albumin	Blood	Serum β -human chorionic gonadotropin†
Hemoglobin	Alkaline phosphatase	Glucose	(β -hCG)†
Platelet count	Alanine aminotransferase (ALT)	Protein	PT (INR)
WBC (total and differential)	Aspartate aminotransferase (AST)	Specific gravity	aPTT
Red Blood Cell Count	Lactate dehydrogenase (LDH)	Microscopic exam (If abnormal)	Total triiodothyronine (T3)
Absolute Neutrophil Count	Carbon Dioxide ‡	results are noted	Free tyroxine (T4)
Absolute Lymphocyte Count	(CO_2 or bicarbonate)	Urine pregnancy test †	Thyroid stimulating hormone (TSH)
	Uric Acid		PK
	Calcium		
	Chloride		Blood for correlative studies
	Glucose		
	Phosphorus		
	Potassium		
	Sodium		
	Magnesium		
	Total Bilirubin		
	Direct Bilirubin		
	Total protein		
	Blood Urea Nitrogen		

† Perform on women of childbearing potential only. If urine pregnancy results cannot be confirmed as negative, a serum pregnancy test will be required.

‡ If considered standard of care in your region.

Laboratory tests for screening or entry into the Second Course Phase should be performed within 7 days prior to the first dose of treatment. After Cycle 1, pre-dose laboratory procedures can be conducted up to 72 hours prior to dosing. Results must be reviewed by the investigator or qualified designee and found to be acceptable prior to each dose of trial treatment.

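### The scheduled blood counts cannot establish the hematologic DLT, which biases the 50 to 60 mg/m² doxorubicin decision toward escalation

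*Combined protocol and SAP*

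**What the plan says.** **The criterion.** Section 8.1.2 has one entry under its hematologic heading, "Any Grade 4 thrombocytopenia or neutropenia lasting >7 days". It applies to both cohorts. To be evaluable, a patient must complete one course and "be observed for at least 21 days after the start of the first course or have experienced a DLT"; no blood count is named as a condition. The note under the Section 8.1.3 table defines a DLT patient as "a patient with a documented first-cycle DLT", and a PASS as a fully evaluable patient without one.

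**The schedule.** In the Section 6.1 flow chart the row "CBC with Differential" has one mark at screening, one per treatment cycle and one at safety follow-up. There is no mid-cycle column. Section 5.3.2 fixes the order within a cycle: "Trial treatment should be administered on Day 1 of each cycle after all procedures/assessments have been completed as detailed on the Trial Flow Chart". It also gives a dosing window: "Trial treatment may be administered up to 3 days before or after the scheduled Day 1 of each cycle due to administrative reasons". Section 7.1.2.7 adds: "After Cycle 1, pre-dose laboratory procedures can be conducted up to 72 hours prior to dosing". I found no extra counts for lead-in patients anywhere in the document.

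**The decision.** Under Sections 8.1.1 and 8.1.3, doxorubicin goes from 50 to 60 mg/m² after 0 DLTs in 3 evaluable patients or 1 in 6. Two DLTs send the next patient to a lower level.

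**The concern.** A criterion defined by duration needs repeated measurement, and the schedule supplies almost none. Showing from counts that a Grade 4 cytopenia lasted more than 7 days takes at least two post-dose Grade 4 counts more than 7 days apart. Cycle 1 has no such pair. Because only documented events count and no CBC is required for PASS, an unseen event is not treated as missing; it becomes evidence of safety.

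Doxorubicin is the only drug escalated, and Section 10.1.4 itself lists bone marrow damage and infection with low white counts among its toxicities. The chosen level carries forward as Cohort 1 accrues to 36 patients. Section 2.1 promises an interim look at safety in this cohort, but Section 8 gives no later rule for re-testing the dose.

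**Working it through.** The documents state no operating characteristics for the lead-in, so there is no published figure to reproduce. I made two checks.

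**1. Calendar**

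- Scheduled counts around cycle 1: Day 1 before any drug, and cycle 2 Day 1, nominally day 22. The gap is 22 − 1 = 21 days.
- Earliest cycle 2 draw: 22 − 3 (dosing window) − 3 (72-hour laboratory window) = day 16. Latest: 22 + 3 = day 25. The gap is therefore 15 to 24 days.
- Scheduled post-dose counts before the cycle 2 draw: none. At that draw: one.
- An 8-day Grade 4 episode starting on day *o* ends on day *o* + 7. For assumed onsets of day 5 to day 14 it ends on day 12 to day 21, so it meets no scheduled count at the nominal day 22. At the earliest draw (day 16), onsets from day 9 on would give one Grade 4 value, which flags the episode but does not date it.
- To be Grade 4 at two scheduled post-dose draws (days 22 and 43), an episode would have to last at least 43 − 22 + 1 = 22 days, and the second draw is outside cycle 1.

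**2. Effect on the escalation rule**

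I treat the Section 8.1.3 table as a decision after 3, and if needed after 6, evaluable patients, ignoring those still at risk when the third is evaluated. With *p* the chance that a patient is recorded as a DLT:

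P(escalate) = (1 − *p*)³ + 3*p*(1 − *p*)⁵

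*p* = 1 − (1 − *pn*)(1 − *s*·*ph*)

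Here *ph* is the true rate of Grade 4 cytopenia lasting more than 7 days, *pn* the rate of other DLTs (taken as independent), and *s* the share of the cytopenias that is documented. **All three are assumptions; none is in the documents.** With *pn* = 10%:

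| *ph* | all documented (*s* = 1) | half (*s* = 0.5) | none (*s* = 0) |
|---|---|---|---|
| 10% | *p* = 0.190, 73% | *p* = 0.145, 82% | *p* = 0.100, 91% |
| 20% | *p* = 0.280, 54% | *p* = 0.190, 73% | *p* = 0.100, 91% |
| 30% | *p* = 0.370, 36% | *p* = 0.235, 63% | *p* = 0.100, 91% |

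Example: for *ph* = 20% and *s* = 1, *p* = 1 − 0.9 × 0.8 = 0.28, and 0.72³ + 3 × 0.28 × 0.72⁵ = 0.373 + 0.163 = 0.536.

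With *pn* = 5% the rows run 82.4%, 62.2%, 42.5% (all documented) and 91.0%, 82.4%, 72.5% (half), against 97.3% (none).

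**The case against.** The strongest reply is that the schedule is a minimum.

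- **Unscheduled tests.** Section 7.1 allows procedures at unscheduled times if the investigator judges them clinically necessary, and Section 7.1.2.1 allows more frequent AE assessment. Nothing limits this to patients with symptoms.
- **Outside guidance.** Section 7.1.1.8 has doxorubicin prescribed according to its label and practice guidelines, and Section 5.3.3 refers to the package insert for dose adjustment. Those sources may or may not call for interim counts; the protocol does not reproduce them.
- **Other routes to a DLT.** A Grade 3 or 4 complication such as infection, or a delay of more than 2 weeks caused by a treatment-related event, is itself a DLT under Section 8.1.2.

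These points stand, and they rule out the stronger reading that the lead-in cannot observe hematologic DLTs at all. They narrow the gap to episodes that recover before the cycle 2 draw with no extra counts and no other DLT. They do not close it. Unscheduled testing is discretionary, so detection can differ between patients and dose levels. The delay rule misses a patient who has recovered by cycle 2, and a delay of more than 2 weeks is known only after day 22 + 14 = 36, well past the 21-day minimum.

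The criterion can also be read as Grade 4 thrombocytopenia of any duration, with the 7 days attached to neutropenia alone. A transient fall between the two draws would still go unseen.

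**Conclusion.** The point holds in this form: the scheduled CBCs cannot establish the hematologic DLT as defined, and the resulting error runs only toward escalation.

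Under the assumed rates with *pn* = 10%, the chance of escalating rises by about 9, 19 or 27 percentage points if half the events are documented, and by about 18, 37 or 55 points if none are. A reader might take the last set as the expected effect. The documents do not support that: they give no rate of prolonged Grade 4 cytopenia, and the discretionary and secondary routes make zero detection a worst case. Nor do they support an inference that 60 mg/m² is unsafe or would be wrongly chosen. The finding is about what the rule can determine, not about the dose.

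The calendar argument needs no assumed rate; only the size does. Cohort 2 shares the definition and the schedule, but the consequence lies mainly in Cohort 1, where the dose is escalated. The response-rate decision rules in Section 8.2 are unaffected. This should be corrected, since it concerns the plan's only dose-selection rule and is cheap to fix.

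**What to change.** Reconcile Section 6.1 with Section 8.1.2 for lead-in patients, in one of two ways:

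1. make the cycle 1 CBC schedule able to determine the stated duration criterion, with enough counts to bound the start and end of a Grade 4 episode; or
2. state the hematologic criterion in terms that the scheduled counts can determine, and say openly that the lead-in does not assess nadir duration.

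In either case, state in Sections 8.1.2 and 8.1.3 which counts must be available before a patient is classed as PASS, and make clear whether the 7-day duration applies to thrombocytopenia. The choice of schedule or criterion is a clinical one for the sponsor and investigator.

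**Cost.** The first route means a few extra routine counts in about 6 to 12 Cohort 1 lead-in patients (two levels, 3 to 6 evaluable patients each). No existing draw can be assumed to cover them. Section 4.1.5.2 says "blood samples will be obtained at weeks 0, 2, 4, 6, 8, 10, 20, and 30", but these are correlative samples, and the flow-chart footnote omits week 2 and makes the other weeks subject to patient agreement. The second route costs only wording, at the price of a lead-in that admits it does not measure how long counts stay low.

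### A dose delay of more than two weeks is a DLT, but a patient can be passed as DLT-free 15 days before such a delay can be established

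*Combined protocol and SAP*

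**What the plan says.** Section 8.1.2 lists the DLTs for both cohorts. Most are defined by grade. One is defined by time: "Discontinuation or delay of more than 2 weeks of any study drug due to treatment-related AE will be considered as a DLT".

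The same section sets the evaluability rule. The patient must receive one complete course and "be observed for at least 21 days after the start of the first course or have experienced a DLT".

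The note to the table in Section 8.1.3 defines the statuses that drive the decision:

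- DLT is "a patient with a documented first-cycle DLT".
- PASS is "a patient without a first-cycle DLT fully evaluable for toxicity for the purpose of dose escalations".
- At Risk is "a patient who is on study in the first cycle and not yet DLT, PASS, or Inevaluable".
- EVAL is DLT or PASS.

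In that table, 0 DLT with 3 EVAL, or 1 DLT with 6 EVAL, leads to "Accrue next patient at the next higher level". Two DLTs lead to "Accrue next patient at the next lower level to a maximum of 6". In Cohort 1, going below the starting doxorubicin dose "will require discussion with the sponsor and an amendment" (Section 8.1.1.1.1).

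Section 8.1.1.1.2 releases Cohort 2 to phase II accrual once the first 6 patients have finished cycle 1 with no more than 1 DLT. It holds accrual if 2 DLTs occur in those 6.

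Table 2 (Section 5.3) and Section 5.3.2 place both intravenous drugs on the first day of each 3-week cycle.

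**The concern.** The time-based criterion and the evaluability rule run on different clocks. A patient who has completed the first dose can meet the delay criterion for an every-3-week drug only through a late second dose. By the time that delay is long enough to count, the patient may already have been classed as PASS, and the event may be read as falling outside the first cycle. The plan calls the event a DLT but provides no step that puts it into the count.

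Such events are foreseeable. Table 3 (Section 5.3.1.2) holds pembrolizumab at Grade 2 for diarrhea/colitis, raised AST/ALT/bilirubin, hypophysitis, pneumonitis, and renal failure/nephritis. None of these is a DLT by grade at Grade 2. Footnote 2 also allows holds for other intolerable or persistent Grade 2 events. For these toxicities Table 3 allows up to 12 weeks from the last dose for resolution, so holds that run past day 36 are contemplated.

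At stake are the decision to escalate doxorubicin in Cohort 1 and the decision to open Cohort 2 to full accrual.

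**Working it through.** The documents state no DLT rate and no operating characteristics for the lead-in, so there is no plan figure to reproduce. The finding rests on steps 1 and 2; steps 3 and 4 give its size.

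**1. Dates.** Inputs: 3-week cycle (Table 2), PASS allowed from 21 days, delay limit of more than 2 weeks (Section 8.1.2).

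- Second dose due: 21 days after the first.
- Delay of more than 14 days first true, in whole days: 21 + 15 = 36 days.
- Gap: 36 − 21 = 15 days.

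Counted to the moment rather than in whole days, the limit is passed just after 21 + 14 = 35 days. If the 3-day administrative window in Section 5.3.2 is allowed first, it is passed after 38 days. The gap is at least 14 days on any of these conventions.

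**2. Effect on the action.** The Section 8.1.3 table is read with one patient at level 1 whose second dose is on hold.

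| Status of held patient | Third to be classified, no DLT so far | Sixth to be classified, one DLT so far |
|---|---|---|
| PASS | 0 DLT/3 EVAL: escalate | 1 DLT/6 EVAL: escalate |
| At Risk | 0 DLT/2 EVAL: stay, or hold if 5 are on the level | 1 DLT/5 EVAL, 6 on the level: hold accrual |
| DLT | 1 DLT/3 EVAL: stay | 2 DLTs: next lower level, which here needs an amendment |

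In Cohort 2, if one DLT has already occurred among the first 6, the same patient separates a successful lead-in (1 of 6) from an accrual hold (2 of 6).

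**3. Size if delays are counted, but late.** Expected accrual in the gap = patients / (months × 30.44) × 15 days, using the accrual plans in Sections 8.2.1 and 8.2.2.

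- Cohort 1: 36/(24 × 30.44) × 15 = 0.74, to 36/(18 × 30.44) × 15 = 0.99.
- Cohort 2: 20/(24 × 30.44) × 15 = 0.41, to 20/(12 × 30.44) × 15 = 0.82.

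**4. Size if delays are never counted (illustration).** Assumptions not in the documents: true DLT rate 20% or 33%, with 10% or 25% of DLTs being delay-only. The level 1 rows were simulated up to the first escalate or de-escalate decision, with 40,000 runs per setting and Poisson accrual. Accrual was 1.5 or 2.0 patients per month (36/24 and 36/18). Grade-based DLTs were uniform over days 0–21. Delay-only patients were either At Risk until day 36 and then DLT, or PASS at day 21.

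| DLT rate | Delay-only share | P(escalate), counted → never counted, 1.5/month | Same, 2.0/month |
|---|---|---|---|
| 20% | 10% | 0.698 → 0.738 | 0.699 → 0.741 |
| 20% | 25% | 0.706 → 0.800 | 0.705 → 0.802 |
| 33% | 10% | 0.415 → 0.479 | 0.421 → 0.479 |
| 33% | 25% | 0.430 → 0.588 | 0.424 → 0.586 |

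The differences run from 4 to 16 percentage points. A closed-form check treats the rule as 0/3, or 1/3 then 0/3: P = (1−q)³ + 3q(1−q)⁵, with q = rate × (1 − share). At 20% and a 10% share, q goes from 0.20 to 0.18 and P from 0.709 to 0.752. At 33% and 25%, q goes from 0.33 to 0.2475 and P from 0.434 to 0.605. Both agree in direction and approximate size.

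For Cohort 2, the chance of at most 1 DLT in 6 is (1−q)⁶ + 6q(1−q)⁵. It rises from 0.655 to 0.704 in the first setting and from 0.358 to 0.540 in the second.

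**The case against.** The strongest reply is that the text can be read consistently. The 21 days are a minimum, PASS is permitted then but not required, and the first cycle has no stated end. A patient who has not received the second dose could be regarded as still in cycle 1, and so At Risk. The rash exclusion in Section 8.1.2, which depends on recovery by the next pembrolizumab dose, suggests that readiness for dose 2 was in mind. The delay criterion is itself mandatory, and nothing bars adding a late DLT to the count. The table also tolerates pending outcomes, since it escalates at 0 DLT/3 EVAL with up to two further patients unresolved.

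That reading is open but not stated. Table 2 describes a 3-week cycle, which supports the other one, and the two lead to different actions. Tolerating patients who are labelled At Risk is not the same as labelling a held patient PASS.

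Several limits do stand:

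- The trigger is narrow. It needs a treatment-related event that is not a DLT by grade, delays an every-3-week drug by more than two weeks, and occurs in a patient who decides the row. Discontinuation, or an aromatase inhibitor hold that starts early, can be seen within 21 days.
- The Cohort 2 hold for 2 DLTs in 6 carries no first-cycle limit, which partly offsets the gap there.
- The simulated differences depend on the assumed share; at a 5% delay-only share they shrink to roughly 1 to 3 points.
- Table 3 still governs each patient's own treatment, and the protocol management team monitors safety. However, Section 7.2.4 requires only that escalation decisions be noted in the report sent to the DSMC.

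**Conclusion.** The point holds and should be fixed. As written, the 21-day and first-cycle rules allow escalation or release while an event that the plan itself defines as a DLT is uncounted, and no section says how a held patient is classified in the meantime. The firm part is the 15-day gap (whole-day counting from the first dose) and the fact that one patient is enough to change the action. The practical effect is about one extra patient or fewer per cohort if delays are counted late. If they are never counted, it is 4 to 16 percentage points on the chance of escalating, under assumed DLT rates of 20–33% and delay-only shares of 10–25%. This is a gap in the decision rule for delay-only events of the every-3-week drugs, not a loss of all protection.

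**What to change.** Reconcile the delay criterion and the 21-day rule in Section 8.1.2 with the first-cycle wording in Sections 8.1.1.1 and 8.1.1.1.2 and in the note to the Section 8.1.3 table. The reconciled text should state:

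1. One status (At Risk, PASS or DLT) for a patient whose second dose is on hold for a treatment-related adverse event when a dose-level or release decision falls due.
2. Whether a delay established after day 21 counts in that decision, including whether a PASS can be changed to a DLT.

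The length of the DLT window, the content of the DLT list and the hold rules are for the sponsor to decide.

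The cost is wording in up to four places. If the sponsor chooses to keep held patients At Risk, their classification comes 15 days later, and only theirs.
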